9.1.2 Statistical Power

The precision of the estimates of AUC_{0-∞} and C_{24hr} will be assessed by calculating the half-width of the 95% confidence intervals expected for the given sample size and assumed variability. Assuming a true standard deviation of 0.367 log-[μ M•hr] and 0.590 log-[nM] for natural log-AUC_{0-∞} and C_{24hr} between subjects as obtained from Study 812, then the half-width of the 95% confidence interval for the true mean AUC_{0-∞} and C_{24hr} on the natural log scale will be 0.233 log-[μ M•hr] and 0.375 log-[nM]. The lower and upper 95% confidence limits for the true geometric mean AUC_{0-∞} and C_{24hr} will be given by OBS/1.263 and OBS × 1.263, OBS/1.455 and OBS × 1.455, where OBS is the observed geometric mean. Thus, for example, if the observed geometric mean AUC_{0-∞} was 50.1 [μ M•hr] and C_{24hr} was 41.6 [nM], the 95% confidence interval would be 39.7 to 63.3 [μ M•hr] and 28.6 to 60.5 [nM], respectively.

9.2 Statistical Analysis Plan

Statistical analysis of data obtained in this study will be performed or supervised by the biostatistics department under cooperation of the translational pharmacology department. Once the study is initiated, any changes to the statistical analysis plan described below will be documented in the clinical study report along with the reasons for the changes.

9.2.1 Hypotheses/Estimation

See "3. Hypotheses, Objectives, and Endpoints."

Post-marketing Clinical Study Protocol Number-Version Number: 851-00

9.2.2 Endpoints

Primary endpoints are all AEs, laboratory test results, 12-lead ECGs, and vital signs.

Secondary endpoints are plasma MK-0518 concentrations and pharmacokinetic parameters (AUC_{0- ∞}, C_{max}, C_{24hr}, T_{max}, apparent t_{1/2}, CL/F, and Vz/F).

9.2.3 Analysis Populations

This section defines analysis populations. Data for all participants will be analyzed based on the treatment group in which individual participants have received administration.

All Subjects as Treated (AST): The set of all participants who have received at least 1 dose of the study drug, to be used for safety and tolerability evaluations.

Per-Protocol (PP): A subset of participants meeting the protocol criteria likely to provide data that sufficiently reflect efficacy under the scientific model. Protocol adherence will be determined by measures such as the exposure to study drug, the availability of measurements, and the absence of significant protocol deviations. Significant protocol deviations will be identified by the personnel involved in the collection, analysis, and interpretation of data. The data of all participants excluded from analysis will be identified and documented in the clinical study report along with the reasons for exclusion. This set of participants will be included in the pharmacokinetic analysis.

9.2.4 Statistical Methods

Safety

Summary statistics of the measured values and their changes from baseline will be provided for laboratory test results, 12-lead ECGs, and vital signs together with a graph as appropriate. The changes from baseline will be shown, calculated with the scales of measurements (actual changes from baseline), or calculated on the natural log scale and back transformed (percent changes from baseline), depending on safety variables.

Summary Statistics

Pharmacokinetic parameters for each participant will be listed, for which the number of participants (the number of participants with no missing measurements), arithmetic mean, standard deviation, percent CV ($100 \times \text{standard deviation/arithmetic mean}$), median, minimum, maximum, geometric mean, and geometric percent CV ($100 \times \text{sqrt (exp (s2)} - 1$) will be calculated. The s2 here denotes an estimate of variance on the natural log scale. AUC_{0-\infty}, C_{max}, and C_{24hr} will be natural log transformed, and mean 95% confidence intervals will be calculated based on the t distribution. The confidence interval of geometric means will be provided with the scale of measurement by taking the lower and upper 95% confidence limits.

Post-marketing Clinical Study Protocol Number-Version Number: 851-00

Analysis of the pharmacokinetic similarity between Japanese and non-Japanese populations

For the analysis of pharmacokinetic similarity between Japanese and non-Japanese populations, pharmacokinetic parameters for a single dose of MK-0518 in Japanese and non-Japanese participants (Studies 812 and 824) will be compared in an exploratory manner. Pharmacokinetic parameters including $AUC_{0-\infty}$, C_{max} and T_{max} will be provided in graphs by race. $AUC_{0-\infty}$, C_{24hr} and C_{max} will be natural log transformed, for which geometric mean ratios and 90% confidence intervals will also be calculated based on the t distribution with a linear model having ethnicity (Japanese/non-Japanese) as a term.

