2.3 Benefits/Risks

The study is planned for the purpose of collecting information related to the safety and efficacy of the study drug. Therefore, it cannot be guaranteed that the study participants will obtain benefits directly from the treatment during the study period.

Since this study is conducted in healthy participants, the administration of MK-0518 is not likely to bring benefits to their health.

Refer to the package insert and Pharmaceutical Interview Form of ISENTRESS® Tablets 600 mg for the benefits and risks of participating in this study.

Post-marketing Clinical Study Protocol Number-Version Number: 851-00

3 Hypotheses, Objectives, and Endpoints

This study will be conducted in healthy Japanese male participants.

| Objectives/hypotheses | Endpoints |
|--|--|
| Primary | |
| Objective: To evaluate the safety and tolerability of MK-0518 when administered at a single oral dose of 1200 mg in healthy Japanese male participants Hypothesis (H1): None | Physical findings Vital signs (blood pressure, pulse rate, respiratory rate, body temperature [axillary]) Laboratory tests (hematology, clinical chemistry, urinalysis) 12-lead ECGs Adverse events (clinical symptoms/laboratory test values) |
| Secondary | |
| Objective: To obtain plasma pharmacokinetic data (e.g. AUC₀-∞, Cmax, C₂₄hr, Tmax, and apparent t₁/₂) of MK-0518 1200 mg when administered as a single oral dose Hypothesis (H2): To estimate the geometric mean ratio of plasma pharmacokinetic data (AUC, Cmax, and C₂₄hr) of a single oral dose of MK-0518 1200 mg in Japanese participants retrospectively compared with non-Japanese populations | • Plasma MK-0518 concentrations and pharmacokinetic parameters (AUC _{0-∞} , C _{max} , C _{24hr} , T _{max} , apparent t _{1/2} , CL/F, and Vz/F) |

4 Study Design

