4.3 Justification for Dosing Regimen of the Study Drug

4.3.1 Starting Dose for This Study

Following the non-Japanese phase 1 clinical study that had demonstrated an improvement in the bioavailability of newly formulated raltegravir 600 mg tablets, a non-Japanese phase 3 clinical study in HIV treatment-naive patients (ONCEMRK) demonstrated the noninferiority of raltegravir 1200 mg (600 mg tablet \times 2) once daily to raltegravir 400 mg twice daily. On the basis of these study results and data from 3 drug interaction studies, the dosage and administration of raltegravir 1200 mg (600 mg tablet \times 2) once daily was approved in Japan. The approved dose of 1200 mg (600 mg tablet \times 2) was selected as the dose for this study.

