9.2.6 Sample Size and Power Calculations

Precision of Pharmacokinetic Parameters

The precision of the estimates of $AUC_{0-\infty}$ and C_{24hr} will be assessed by calculating the half-width of the 95% confidence intervals expected for the given sample size and assumed variability. Assuming a true standard deviation of 0.367 log-[μ M•hr] and 0.590 log-[nM] for natural log- $AUC_{0-\infty}$ and C_{24hr} between subjects as obtained from Study 812 in 12 subjects receiving raltegravir, then the half-width of the 95% confidence interval for the true mean $AUC_{0-\infty}$ and C_{24hr} on the natural log scale will be 0.233 log-[μ M•hr] and 0.375 log-[nM]. The lower and upper 95% confidence limits for the true geometric mean values will be given by OBS/1.263 and OBS × 1.263, OBS/1.455 and OBS × 1.455, where OBS is the observed geometric mean. Thus, for example, if the observed geometric mean $AUC_{0-\infty}$ was 50.1 [μ M•hr] and C_{24hr} was 41.6 [nM], the 95% confidence interval would be 39.7 to 63.3 [μ M•hr] and 28.6 to 60.5 [nM], respectively.

Post-marketing Clinical Study Protocol Number-Version Number: 851-00

10 Appendices (Supporting Documentation and Operational Considerations)

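### Does the exploratory Japanese/non-Japanese exposure ratio need its reference records and its expected precision written into the plan?

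*Combined protocol and SAP*

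**What the plan says.** Section 3 (repeated in Section 1.1) sets H2 as estimating the geometric mean ratio of AUC, Cmax and C24hr for a single oral 1200 mg dose "in Japanese participants retrospectively compared with non-Japanese populations". Section 9.2.1 sends the reader back to that statement.

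Section 9.2.4 names the source of the reference data: "pharmacokinetic parameters for a single dose of MK-0518 in Japanese and non-Japanese participants (Studies 812 and 824) will be compared". It calls the comparison exploratory. AUC0-∞, C24hr and Cmax are log transformed, and the ratio and its 90% interval come from the t distribution "with a linear model having ethnicity (Japanese/non-Japanese) as a term". Section 9.2.5 says that no hypotheses are defined for testing.

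Section 9.2.3 defines the Per-Protocol set for this study's participants and adds: "This set of participants will be included in the pharmacokinetic analysis". Section 9.2.6 takes log-scale SDs of 0.367 (AUC0-∞) and 0.590 (C24hr) "as obtained from Study 812 in 12 subjects receiving raltegravir" and reports "the half-width of the 95% confidence interval for the true mean" of each parameter in one group. Section 9.2 adds that, once the study has started, "any changes to the statistical analysis plan described below will be documented in the clinical study report along with the reasons for the changes".

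**The concern.** All the Japanese data come from this study and, on the natural reading, all the reference data come from Studies 812 and 824. H2 is therefore a contrast between studies, and its value depends on which earlier records form the denominator. Section 9.2.4 gives no arm or period, food state, number of participants or analysis set for them. Study 824 is named nowhere else. Study 812 otherwise appears only as the source of the two SDs, and the reference list is marked not applicable. Section 4.3.1 also mentions a phase 1 formulation study and "data from 3 drug interaction studies", and Section 4.3.3 mentions five-day repeat dosing, without saying which of these, if any, are 812 or 824.

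The worry is about freedom of choice. Study 812 results are already in hand and this study is open-label. Section 9.2 asks for documentation of changes to what the plan describes. A reference set that was never described could be settled after the Japanese concentrations are known without counting as a change. Separately, a reader of Section 9.2.6 is not told how wide the interval for the ratio will be, nor given any precision for Cmax. The Japanese pharmacokinetic study was a condition of approval (Section 2.1), and this ratio is the plan's only model-based comparison between populations.

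**Working it through.** **What the text leaves open about the reference records**

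| Item | Where it can be found |
|---|---|
| Source studies | Named in 9.2.4: 812 and 824 |
| Dose | Single 1200 mg, from H2 in Section 3, reached through 9.2.1 |
| Formulation, food state, health status | Indicated in 4.3.2: 600 mg tablet × 2, fasted healthy non-Japanese adults. This study is also fasted (4.1) |
| Model terms | Ethnicity is the only one named (9.2.4) |
| Arm or period, number, analysis set | Not stated, chiefly for Study 824 |

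The mean AUC0-∞ of 50.1 μM•hr and C24hr of 41.6 nM in Section 4.3.2 are the same values used in the worked example in Sections 9.1.2 and 9.2.6, beside the Study 812 SDs. This suggests, without proving it, that the 4.3.2 benchmark comes from Study 812.

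An unlisted model term is not a serious ambiguity either. If every Japanese participant is in this study and every reference participant in another, a fixed study effect is aliased with ethnicity and could not be added usefully.

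**The plan's own precision figures**

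Inputs: n = 12 (Section 4.1); SDs 0.367 and 0.590 (Section 9.2.6). Half-width = t(0.975, 11) × SD / √12, with t = 2.201.

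- AUC0-∞: 2.201 × 0.367 / 3.464 = 0.233; factor exp(0.233) = 1.263; 50.1 gives 39.7 to 63.3.
- C24hr: 2.201 × 0.590 / 3.464 = 0.375; factor 1.455; 41.6 gives 28.6 to 60.5.

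All match the plan.

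**Precision of the ratio**

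Half-width = t(0.95, 12 + n − 2) × SD × √(1/12 + 1/n), with n reference participants, equal variances and one independent record each. The documents do not clearly give n: the 12 subjects in Section 9.2.6 may describe Study 812 or this study. It is therefore an assumption, shown as a range. For n = 12, AUC0-∞: 1.717 × 0.367 × 0.408 = 0.257.

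| Assumed n | AUC0-∞ half-width | 90% CI at ratio 1 | C24hr half-width | 90% CI at ratio 1 |
|---|---|---|---|---|
| 12 | 0.257 | 0.77–1.29 | 0.414 | 0.66–1.51 |
| 24 | 0.219 | 0.80–1.25 | 0.353 | 0.70–1.42 |
| 36 | 0.205 | 0.81–1.23 | 0.330 | 0.72–1.39 |
| unlimited | 0.174 | 0.84–1.19 | 0.280 | 0.76–1.32 |

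An unlimited reference group would still leave 0.174 / 0.257 = 68% of the half-width seen with 12, because the 12 Japanese participants set the floor. The printed one-group factors (1.263 and 1.455) lie within the ranges for the ratio (1.19 to 1.29 and 1.32 to 1.51), so a reader who took them as a rough guide would not be far out. No SD is given for Cmax, so no figure can be shown for it.

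**The case for a change.** The best case for a change is that calling an analysis exploratory removes the test but not the duty to say what is being compared. A few lines naming the arms, numbers and analysis sets would cost almost nothing, would close off any choice made after seeing the data, and would bring later departures under the documentation rule in Section 9.2. A sentence saying that study and ethnicity cannot be separated would also keep readers from over-reading the interval.

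Part of this stands. The arm or period, number and analysis set are not in the documents, and the link between Section 4.3.2 and Study 812 is only an inference. The interval also takes no account of differences between studies.

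The argument about choice is weaker. If the worry is that Study 824 might be left out, the plan already names it, so leaving it out is a change that must be documented. If the worry is about alternative records within 812 or 824, nothing in the documents shows that a second set matching a single fasted 1200 mg dose exists. Any estimate of how far the ratio could move rests on an assumed block of optional records. Counting how often the interval would gain or lose the value 1 uses a criterion that the plan never applies. The open-label design adds little, since the parameters are calculated from measured plasma concentrations. As for confounding, Section 3 already describes the comparison as retrospective, which signals its historical nature.

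**Conclusion.** No change to the plan follows. This is missing detail that an analyst would fill sensibly: H2 gives the dose, Section 4.3.2 points to the formulation and fasted state, and Section 9.2.4 gives the studies, scale, parameters, interval and model term. A sponsor that took the matching single-dose records would carry out the same analysis with or without the extra wording.

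The missing precision statement is an omission, not a wrong figure. A reader can derive it from the printed SDs: the expected 90% interval at a ratio of 1 is no wider than about 0.77–1.29 for AUC0-∞ and 0.66–1.51 for C24hr if there are at least 12 reference participants. Those widths assume the Study 812 SDs apply to both groups, independent records and no variation between studies. No test, margin or decision depends on them.

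The conclusion would be different if Studies 812 and 824 held several equally eligible single-dose 1200 mg data sets, or if a similarity criterion were attached to the ratio. The documents show neither. Naming the records used, and noting that study and ethnicity are confounded, is ordinary content for the clinical study report.

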4.1 Study Design Outline

This is an open-label single oral dose study in healthy Japanese male participants comprising a single panel. A total of 12 participants will receive 1200 mg of MK-0518 under fasting conditions.

Study procedures including visit frequency during the study period and the acceptable range of visits are outlined in "1.3 Study Schedule." Details of each procedure are provided in Section 8.

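### The 90% interval for the Japanese/non-Japanese ratio has no stated variance structure; the default single pooled variance miscalibrates it if the groups are unbalanced and their SDs differ

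*Combined protocol and SAP*

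**What the plan says.** Section 3 (H2) sets out to estimate the geometric mean ratio of AUC, Cmax and C24hr between Japanese participants and non-Japanese populations. Section 9.2.4 supplies the method: on the log scale, the ratios and their 90% limits are "calculated based on the t distribution with a linear model having ethnicity (Japanese/non-Japanese) as a term". No other model term, no variance structure and no degrees-of-freedom method is named.

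On group sizes, Section 4.1 states "A total of 12 participants will receive 1200 mg of MK-0518 under fasting conditions". The comparator is "participants (Studies 812 and 824) will be compared in an exploratory manner". Neither the size of Study 824 nor the combined comparator N is given.

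On variability, Section 9.2.6 gives log-scale SDs of 0.367 (AUC0-∞) and 0.590 (C24hr), described as "between subjects as obtained from Study 812 in 12 subjects receiving raltegravir". The 12 there could be the size of Study 812 or the n used for this study's own precision calculation. No SD is given for Japanese participants, for Study 824 or for Cmax. Section 9.2.5 says that the study has no hypotheses to test, and no similarity bounds are given.

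**The concern.** A linear model with a two-level group term and t-based limits, fitted with default settings, estimates one residual variance with n1+n2−2 degrees of freedom. When one group is larger, that estimate is weighted towards the larger group, while the uncertainty of the contrast comes mostly from the smaller one. If the smaller group is the more variable, the interval is too narrow; if it is the less variable, the interval is too wide. With equal group sizes the two effects cancel almost exactly.

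Imbalance is likely here but not documented. If Study 812 contributed 12 participants, any participant from Study 824 takes the comparator above 12. Equal SDs cannot be verified from the documents either. The Japanese group is men aged 20 to 45 at one site, whereas the comparator merges two studies.

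What is at stake is the calibration of the interval that answers H2. With no test and no bounds, the ratio and its interval are the whole quantitative answer to that objective.

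**Working it through.** **The plan's own figure.** The only precision figures are for the single-group 95% interval: t(0.975, 11) × SD/√12, with t = 2.201.
- AUC0-∞: 2.201 × 0.367/√12 = 0.233; exp(0.233) = 1.263; 50.1/1.263 to 50.1 × 1.263 = 39.7 to 63.3.
- C24hr: 2.201 × 0.590/√12 = 0.375; exp(0.375) = 1.455; 41.6/1.455 to 41.6 × 1.455 = 28.6 to 60.5.

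Both match Section 9.2.6. No precision figure is stated for the ratio.

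**Inputs for the ratio.** From the documents: n1 = 12 Japanese; 90% two-sided t interval; non-Japanese SD σ = 0.367 or 0.590. Assumed, because the documents give neither: comparator n2 from 12 to 60, and Japanese/non-Japanese SD ratio r from 0.67 to 1.5.

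**Formulas.**
- True variance of the log-mean difference: σ²(r²/n1 + 1/n2).
- Expected pooled estimate: σ² × [(n1−1)r² + (n2−1)]/(n1+n2−2) × (1/n1 + 1/n2).

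At 12 vs 12 both equal σ²(r²+1)/12, so the pooled standard error is right on average for any r. At 12 vs 24, in units of σ²:

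| r | Expected pooled variance | True variance | SE ratio, √(pooled/true) |
|---|---|---|---|
| 0.67 | 0.1027 | 0.0791 | 1.14 |
| 0.8 | 0.1104 | 0.0950 | 1.08 |
| 1 | 0.1250 | 0.1250 | 1.00 |
| 1.25 | 0.1477 | 0.1719 | 0.93 |
| 1.5 | 0.1756 | 0.2292 | 0.88 |

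**Coverage.** Simulated with 400,000 normal replicates per scenario. Coverage depends on n2 and r but not on σ. Pooled-variance 90% interval:

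| n2 | r = 0.67 | r = 0.8 | r = 1 | r = 1.25 | r = 1.5 |
|---|---|---|---|---|---|
| 12 | 89.9% | 89.9% | 90.0% | 89.9% | 89.8% |
| 24 | 93.7% | 92.3% | 89.9% | 87.3% | 85.0% |
| 36 | 95.2% | 93.4% | 90.0% | 85.9% | 82.2% |
| 60 | 96.7% | 94.3% | 90.0% | 84.5% | 79.3% |

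At 12 vs 12 a two-fold SD difference still gives about 89.5%. The Welch interval stays at about 90% in every scenario.

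**Size on the ratio scale (12 vs 24).** Worked case, C24hr with r = 1.5, so the Japanese SD is 0.885:
- Pooled variance = (11 × 0.7832 + 23 × 0.3481)/34 = 0.4889. Half-width = 1.691 × √(0.4889 × 0.125) = 0.418, a factor of 1.519.
- Welch variance = 0.7832/12 + 0.3481/24 = 0.0798, with 16.1 degrees of freedom. Half-width = 0.493, a factor of 1.637.

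| Parameter | r | Pooled factor | Welch factor |
|---|---|---|---|
| AUC0-∞ | 0.67 | 1.220 | 1.191 |
| AUC0-∞ | 1 | 1.245 | 1.250 |
| AUC0-∞ | 1.5 | 1.297 | 1.359 |
| C24hr | 0.67 | 1.377 | 1.325 |
| C24hr | 1 | 1.423 | 1.431 |
| C24hr | 1.5 | 1.519 | 1.637 |

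**Price if the SDs are equal.** Median half-width for C24hr, pooled vs Welch: 0.349 vs 0.351 at N=24 (about 1%) and 0.309 vs 0.318 at N=60 (about 3%).

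**The case against.** The strongest reply is that each premise is inferred. Section 9.2.4 does not say that the variance is common, and the comparator N is never given. A reader might conclude that the planned interval is wrong, or that the Japanese SD must be the smaller one because the group is homogeneous. The documents support neither. They contain no evidence that the SDs differ; Section 9.2.6 plans with the Study 812 SDs for the Japanese group; and Section 4.3.2 reports similar single-dose 400 mg pharmacokinetics in fasted Japanese men and non-Japanese. The age range and sites of Studies 812 and 824 are not described, so homogeneity cannot be compared. Nor is the interval off whenever the SDs differ: at equal group sizes it is essentially correct. All of this stands.

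The larger errors also need the more extreme scenarios; at 12 vs 24 with SD ratios of 0.8 to 1.25 the error is 2 to 3 percentage points. That stands too. However, if the Study 812 SD does rest on 12 participants, its own 95% limits run from about 0.71 to 1.70 times the estimate (chi-square, 11 df), so the documents cannot establish equality either.

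The consequence is limited: the comparison is exploratory, without bounds, and the primary objective is safety. The Japanese group's SD, geometric CV and own 95% interval are reported separately, so its variability stays visible.

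Finally, a reader might expect separate variances to cure the pooling of two studies. They do not. With 12 vs 12+12, a within-study SD of 0.59 and an assumed random study effect with SD 0.2 on the log scale, both intervals cover only about 73%.

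**Conclusion.** This holds as a minor specification gap, not a demonstrated error. The plan is silent on variance structure, and its default is the less robust choice if the comparator is larger than 12 and the SDs differ. Under an assumed 12 vs 24, coverage of the nominal 90% interval is about 92% / 87% at SD ratios 0.8 / 1.25 and 94% / 85% at 0.67 / 1.5. The error grows with the comparator N and essentially vanishes at 12 vs 12. The comparator N and the SD ratios are assumptions. No formal conclusion of the study changes. The point concerns only the width of the interval; confounding of ethnicity with study is a separate matter.

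**What to change.** In Section 9.2.4, state that the ethnicity model for log AUC0-∞, Cmax and C24hr is fitted with group-specific residual variances and Satterthwaite degrees of freedom, which gives the Welch interval. Report both groups' log-scale SDs and the comparator N, split by Study 812 and Study 824. Do not let an observed SD difference choose the method: with equal true SDs and 12 vs 24 participants, the observed SD ratio has a 95% range of about 0.56 to 1.62.

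The cost is one sentence in the plan and one program option. If the SDs are in fact equal, intervals are about 1% (N=24) to 3% (N=60) wider. The change leaves between-study differences untouched, and the report should say so.
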